11 STATISTICAL ANALYSIS

11.1 JUSTIFICATION OF THE NECESSARY NUMBER OF PATIENTS

The objective of a non-inferiority study is to demonstrate that the mean difference between the 2 devices remains small and clinically insignificant.

The average blood glucose level achieved in real life with the Omnipod pump is 7.8% according to the experience of the three centers in the scientific committee of the study, which is consistent with the literature. We can assume that the average blood glucose level on the Medtrum pump is the same as on the Omnipod pump.

By setting the Δ threshold for non-inferiority at +0.4%, in accordance with FDA recommendations (Guidance for Industry Diabetes Mellitus (Developing Drugs and Therapeutic Biologics for Treatment and Prevention)), if the upper threshold of the IC95% difference between the 2 pumps (Medtrum-Omnipod) exceeds Δ (i.e., 0.4), non-inferiority will not be demonstrated.

Otherwise, the superiority of the Medtrum pump over the Omnipod pump can be tested, with a Δ' threshold set at -0.3%.

Based on these assumptions, based on the so-called "Less is better" design with $\alpha = 2.5\%$, $\beta = 20\%$, and a standard deviation (SD) set at 0.55, the calculation of the necessary number of (analyzable) subjects is 60 patients (30 in each group).

Assuming that 20% of patients cannot be analyzed (major discrepancies, missing data, lost to follow-up), the number of patients to be randomized is 75. The number of centers to be recruited in 3 months maximum is 6.

To confirm our standard deviation hypothesis, a descriptive analysis of the baseline HbA1c data for the entire population will be performed blinded at the end of the inclusion period. If a large difference from our hypotheses is found, the sample size will be recalculated to maintain 80% statistical power for this study.

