11.2.4 Analysis of the effectiveness / performance of the device

Analysis of primary efficacy endpoint:

The non-inferiority analysis of the primary efficacy endpoint will be performed with an ANOVA, with the DM as an explanatory variable, on the *per protocol* population and then on the *intention-to-treat* population. If the upper bound of the IC95% of the Omnipod-Medtrum estimated difference in means (LSmeans) exceeds the non-inferiority bound, it will be rejected.

Non-inferiority bounds are defined in this protocol and will be used in the statistical analysis plan.

If non-inferiority is demonstrated, a superiority analysis will be conducted.

Secondary efficacy endpoint analyses:

The secondary efficacy endpoints will be analyzed for the variables listed below.

Each variable will be described globally and by pump group.

In case of non-inferiority analysis, the same methodology as for the primary endpoint will be used.

In case of comparison of quantitative variables, parametric (T-test) or non-parametric (Mann-Whitney) tests of comparison of means will be used. In case of comparison of qualitative variables, CHI² or Fisher exact tests will be used.

In case of tests on changes within each group, paired data tests will be used (paired data T-test or Wilcoxon signed ranks test, depending on the distribution of the data).

❖ **HbA1c:**

- Evolution of the value measured in the laboratory from a blood sample taken before the D0 visit and just before the 3-month visit
- Description in the total population, in each group and comparison between groups.

❖ **Glucose measurements**

- Average of glucose measurements over each period and over the entire study duration
- Description of the minimum and maximum values over the total duration of the study
- Description of the % of Time in Range (see ADA and International Consensus on Time in Range recommendations^{25,26})
- Description in the total population, in each group and comparison between groups.

❖ **Glycemic events**

- Description of the number of symptomatic and non-symptomatic hypoglycemic events during the evaluation period, broken down by severity level (see ADA consensus definitions²⁵)
- Description of the number of symptomatic and non-symptomatic hyperglycemia events during the evaluation period, broken down by severity level (see ADA consensus definitions²⁵)
- Description in the total population, in each group and comparison between groups.
-

❖ **Device tolerance**

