5 METHODOLOGY FOR STATISTICAL ANALYSIS

5.1 NUMBER OF SUBJECTS NEEDED (NSN)

The objective of a non-inferiority study is to demonstrate that the mean difference between the 2 devices remains small and clinically insignificant.

The average blood glucose level achieved in real life with the Omnipod pump corresponds to an estimated average HbA1c of 7.8% based on the experience of the three centers in the study's scientific committee, which is consistent with the literature. We can assume that the average blood glucose level on the Medtrum pump is the same as on the Omnipod pump. Setting the Δ threshold for non-inferiority at +0.4%, in accordance with FDA guidance (Guidance for Industry Diabetes Mellitus (Developing Drugs and Therapeutic Biologics for Treatment and Prevention)), if the upper threshold of the IC95% difference between the 2 pumps (Medtrum-Omnipod) exceeds Δ (i.e., 0.4), non-inferiority will not be demonstrated. Otherwise, the superiority of the Medtrum pump over the Omnipod pump can be tested, with a Δ ' threshold set at -0.3%.

On the basis of these assumptions, based on the so-called "Less is better" design with $\alpha = 2.5\%$, $\beta = 20\%$, and a standard deviation (SD) set at 0.55, the calculation of the necessary number of (analyzable) subjects was 60 patients (30 in each group).

Assuming that 20% of patients could not be analyzed (major discrepancies, missing data, lost to follow-up), the number of patients to be randomized was 75.

100 patients were finally included; to confirm our standard deviation hypothesis, a descriptive analysis of baseline HbA1c data for the entire population was performed in a blinded fashion at the end of the inclusion period. The standard deviation of the HbA1c estimate (FSL) was equal to 0.8.

With regard to the other assumptions of the protocol:

- Risk of first kind: 2.5%.
- Statistical power: 80%.
- Non-inferiority limit Δ : +0.4
- Assumed value of the difference between the two pumps: 0

The sample of patients needed for the study is estimated at 63 patients per group, for a total of **126 analyzable patients**.

As the study cannot include more than 100 patients, the statistical power of the study will be less than 80%.

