7.4 ANALYSIS OF THE EVALUATION CRITERIA

7.4.1 Primary endpoint analysis

The primary endpoint is the estimate of HbA1c at 3 months based on the mean of continuous glucose measurements obtained during the last 10 weeks of follow-up.

HbA1c estimation will be described by treatment group and then by type of diabetes.

The non-inferiority analysis of the primary efficacy endpoint will be performed with an ANCOVA, with the medical device as an explanatory variable and an adjustment on the estimate of HbA1c at Baseline, on the PP population.

If the upper bound of the IC95% of the Omnipod-Medtrum estimated difference in means (LSmeans) exceeds the non-inferiority bound set at 0.4, non-inferiority will not be demonstrated.

If non-inferiority is demonstrated, a superiority analysis will be conducted. If the upper bound of the IC95% of the estimated difference in mean is less than -0.3, superiority will be demonstrated.

The MIXED procedure (SAS® 9.4) will be used.

Code:

```
proc mixed data=XX order=data;
where PP = 1;
class DM;
model ESTIM_HBA1c = ESTIM_HBA1c_BASELINE DM;
lsmeans DM / diff=control cl;
run;
```

A sensitivity analysis will be performed on the ITTm population with imputation of missing data by the mean or median according to the distribution of the primary endpoint.

A subgroup analysis will be performed on the population of patients with an LSP wear rate >70% at M3.

Exploratory analysis:

Univariate analyses will be conducted on age in 2 classes (below or above the median), sex, type of diabetes, center, and duration of diabetes in 3 classes (<5 years; between 5 and 10 years; >10 years). If the p-value <0.05, the variable will be included in the full model. Then a top-down stepwise strategy will be conducted to select the variables for the final model.

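### The primary analysis rule applies the upper bound to Omnipod minus Medtrum, the reverse of the design's contrast, so a clearly worse Medtrum pump would be declared non-inferior or even superior

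*SAP*

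**What the plan says.** **Design sections.** Protocol 11.1, the matching part of the protocol summary, and SAP 5.1 agree. Protocol 11.1 puts the "threshold for non-inferiority at +0.4" percentage points and says non-inferiority fails if the upper 95% bound of the "difference between the 2 pumps (Medtrum-Omnipod) exceeds" that margin. SAP 5.1 likewise uses the "upper threshold of the IC95% difference between the 2 pumps (Medtrum-Omnipod"). Both give a superiority threshold of -0.3 and describe a design in which lower values are better.

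**Analysis sections.** Protocol 11.2.4 reverses the subtraction but keeps the upper bound: "If the upper bound of the IC95% of the Omnipod-Medtrum estimated difference in means (LSmeans) exceeds the non-inferiority bound, it will be rejected". It gives no number and takes its margin by reference: "Non-inferiority bounds are defined in this protocol and will be used in the statistical analysis plan". SAP 7.4.1 repeats the reversed contrast and supplies the number: non-inferiority is not shown if the "upper bound of the IC95% of the Omnipod-Medtrum estimated difference in means (LSmeans) exceeds the non-inferiority bound set at 0.4". It then adds: "If the upper bound of the IC95% of the estimated difference in mean is less than -0.3, superiority will be demonstrated". That sentence does not restate the direction, so it inherits Omnipod minus Medtrum from the sentence before it.

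**Code.** The SAP 7.4.1 program requests "lsmeans DM / diff=control cl" under `order=data` and names no control level.

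**Declared changes.** SAP section 6, on changes to the protocol's analyses, says there are none.

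**The concern.** The sign of a non-inferiority contrast and the side of the interval must match. With Medtrum minus Omnipod, a worse Medtrum pump gives a positive difference, and an upper bound below +0.4 rules out a deficit of 0.4 or more. With Omnipod minus Medtrum, a worse Medtrum pump gives a negative difference, so the same upper-bound test becomes easier to pass as Medtrum gets worse. The superiority rule is turned round too: an upper bound below -0.3 on that scale shows that Medtrum is worse by more than 0.3.

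The code does not rescue the text. With levels taken in data order and no control named, the control is whichever pump appears first in the per-protocol file. The sign of the printed difference then depends on how that file is sorted.

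This is the trial's only confirmatory decision rule. Followed literally, it gives almost no type I error control for the claim the trial wants to make, and a truly better Medtrum pump would tend to fail.

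**Working it through.** **Inputs.** Margin +0.4 and superiority threshold -0.3 (Protocol 11.1, SAP 5.1). One-sided alpha 2.5%, power 80%, true difference 0 (SAP 5.1). SD 0.55 at planning and 0.8 at the blinded review (SAP 5.1). 100 patients included (SAP 5.1), 1:1 allocation, 20% not analysable (Protocol 11.1). The figure of 40 analysable per arm is an assumption: 100 × 0.8 / 2.

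**The plan's own sample size.** n per group = 2·SD²·(1.960 + 0.842)² / 0.4².
- SD 0.55: 29.7, so 30 per group. 60 / 0.8 = 75 randomised. Both match the plan.
- SD 0.8: 62.8, so 63 per group. This matches SAP 5.1.

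**Two rules compared.** Let d be the true Medtrum minus Omnipod difference, SE = SD·√(2/n) and c = 1.96·SE (normal approximation, no covariate adjustment).
- Intended: P(non-inferior) = Φ((0.4 − c − d)/SE); P(superior) = Φ((−0.3 − c − d)/SE).
- As written: P(non-inferior) = Φ((0.4 − c + d)/SE); P(superior) = Φ((−0.3 − c + d)/SE).

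With SD 0.8 and n = 40, SE = 0.8·√(2/40) = 0.179 and c = 0.351. At d = +0.4 the rule as written gives Φ((0.4 − 0.351 + 0.4)/0.179) = Φ(2.51) = 99.4%. The intended rule gives Φ(−1.96) = 2.5%.

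| True d (Medtrum − Omnipod) | Non-inferior, intended | Non-inferior, as written | Superior, intended | Superior, as written |
|---|---|---|---|---|
| −0.3 | 97.5% | 8.1% | 2.5% | <0.1% |
| 0 | 60.9% | 60.9% | <0.1% | <0.1% |
| +0.2 | 20.0% | 91.8% | <0.1% | 0.6% |
| +0.4 | 2.5% | 99.4% | <0.1% | 8.1% |
| +0.6 | 0.1% | >99.9% | <0.1% | 38.9% |
| +0.8 | <0.1% | >99.9% | <0.1% | 79.8% |

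In terms of observed means, the rule as written passes non-inferiority unless Medtrum is observed to be better by about 0.05 (0.4 − 0.351) or more. It declares superiority when Medtrum is observed to be worse by more than 0.651 (0.3 + 0.351).

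**Other sizes, rule as written.**
- SD 0.8, 50 per arm (c = 0.314): non-inferiority 99.9% at d = +0.4; superiority 47% at +0.6 and 88% at +0.8.
- SD 0.55, 30 per arm (c = 0.278): non-inferiority 99.99% at +0.4; superiority 56% at +0.6 and 94% at +0.8.

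At d = 0, the value assumed for planning, the two rules have the same power, so the sample-size calculation cannot reveal the reversal.

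**The case against.** The best defence is that this is a transposed pair of names whose intended meaning can be recovered. Three places give the full rule with the right sign, the lower-is-better design fixes the direction of benefit, and Protocol 11.2.4 refers back to the bounds defined in the protocol. The -0.3 threshold also makes sense only as Medtrum minus Omnipod. An analyst who noticed would probably run the correct contrast, and the unnamed control level means the program might produce it anyway. SAP 7.4.1 describes the endpoint by group, so a reversed sign would show beside the arm means, and SAP section 10 requires double programming of the primary analysis.

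Several limits stand. The error rates apply only if the analysis sections are followed literally. Only the SAP attaches -0.3 to an analysis rule. False non-inferiority is near certain for deficits of 0.4 or more but not for small ones (92% at 0.2 with 40 per arm). False superiority becomes likely only for large deficits: 8% at 0.4, 20% at 0.5 and 39% at 0.6.

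None of this removes the fault. The reversed wording is in the governing analysis section of both documents. The hyphen is plainly a minus sign in the design sections, so it cannot be read as a mere label in the analysis sections. Two programmers working from the same sentence can make the same error. The trial is open-label, so a direction left unsettled may have to be chosen when arm-level data can be seen, and either choice departs from some approved text.

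**Conclusion.** The concern holds. The direction of the primary contrast contradicts itself within each document, the analysis wording is the wrong one, and the code does not settle it. Under that wording, with SD 0.8 and an assumed 40 analysable per arm, a Medtrum pump worse by exactly the margin is declared non-inferior 99.4% of the time instead of 2.5%. One worse by 0.8 is called superior 80% of the time, and one better by 0.3 passes 8% of the time instead of 97.5%. These figures use an unadjusted normal approximation. Adjusting for baseline HbA1c would narrow the interval but would not restore the direction. The same pattern appears with 50 per arm and with the planning values. It must be corrected before the primary analysis is run.

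**What to change.** 1. In Protocol 11.2.4 and SAP 7.4.1, define the difference as Medtrum minus Omnipod. In SAP 7.4.1, state that direction in the -0.3 sentence as well as the +0.4 sentence.
2. In the code, name the reference level, for example `lsmeans DM / diff=control('Omnipod') cl;`, with the label matched to the actual coding of DM. The output is then Medtrum minus Omnipod whatever the data order.
3. Record the correction in SAP section 6, before the database is frozen.

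If Omnipod minus Medtrum were kept, the rules would have to use the lower bound, against -0.4 for non-inferiority and +0.3 for superiority. Changing the contrast is simpler and matches the design sections.

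The cost is two wording corrections, one code option and an entry in section 6. No new data or patients are needed, and the calculated sample sizes (30 or 63 per group) do not change.

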Statistical analysis	
Data processing and statistical analysis will be carried out by the service provider, Axonal-Biostatem.
 
The statistical analyses will be described in a Statistical Analysis Plan (SAP) validated by the Sponsor and the Scientific Committee, prior to the freeze-in.
 
Statistical analyses will be performed after baseline freezing of the data with SAS® software (SAS Institute, NC, Cary, USA), version 9.4 or later.
 
Demographic and efficacy/performance analyses will be performed in the ITT population. The primary endpoint will be analyzed in PP (Per Protocol) and then validated in the ITT (intention to treat) population. The safety analyses will be performed in the safety population.
 
For quantitative variables, the usual statistics (n, missing n, mean, standard deviation (SD), median, first and third quartiles (Q1 and Q3), minimum and maximum) will be presented. IC95% may be

	
presented if relevant (especially for the primary endpoint).
 
For categorical variables, the usual statistics (n, missing n, frequency and percentage) for each modality will be provided.
 
Descriptive statistics will be provided in aggregate and by pump group.
 
The type 1 error, α, is set at 5% when the tests used will be two-sided (superiority) and α will be set at 2.5% when the tests will be one-sided in the case of Noninferiority (IC95%).
 
Analysis of the main objective
 
The non-inferiority analysis will be produced via an Ancova or mixed model on the Per-Protocol population and then on an intention-to-treat basis.
 
If non-inferiority is demonstrated, a superiority analysis will be conducted.
 
Analysis of secondary objectives
 
The secondary criteria will be described and then be the subject of mixed or Ancova models.
 
A non-inferiority analysis on HbA1c data and superiority analyses on Time in range, number of glycemic events, patient satisfaction will be performed.

Regulatory framework	ID-RCB number, CPP opinion, CNIL MR001 and RGPD compliance, information to the ANSM, approval of investigator contracts by the CNOM, transparency obligations
Logistics	CRO Axonal-Biostatem (Nanterre, France)

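### The SAP names no population for the superiority test, its only model is per-protocol, and no analysis of patients as randomised has to confirm a superiority claim

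*SAP*

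**What the plan says.** **SAP.** Section 7.4.1 specifies a baseline-adjusted ANCOVA of estimated HbA1c (eHbA1c) in the PP population. For non-inferiority, an upper 95% bound that "exceeds the non-inferiority bound set at 0.4, non-inferiority will not be demonstrated". The next step is "If non-inferiority is demonstrated, a superiority analysis will be conducted", with the rule "If the upper bound of the IC95% of the estimated difference in mean is less than -0.3, superiority will be demonstrated". No population is named for it. The one block of SAS code selects patients with PP = 1. The section then adds a sensitivity analysis in ITTm with mean or median imputation, and does not say that superiority must also hold there. Section 7.1.3 defines ITTm as ITT without four patients discharged because of COVID-19. Full ITT is not used for the primary endpoint. Section 7.1.2 leaves the major or minor grading of deviations to be defined with the sponsor. Section 6, on modifications to the protocol's analyses, says there are none.

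**Protocol.** The summary (Statistical analysis) says "Demographic and efficacy/performance analyses will be performed in the ITT population". Its next sentence sets a specific rule for the primary endpoint: PP first, then validation in ITT. Section 11.2.1 attaches the PP-then-ITT order to the non-inferiority analyses. Section 11.2.4 repeats that order for non-inferiority, then announces a superiority analysis without naming a population. On error rates, the summary says that α "is set at 5% when the tests used will be two-sided (superiority"), which puts 2.5% in Medtrum's direction.

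**The concern.** A programmer following SAP 7.4.1 would read superiority from the PP confidence interval, because no other interval is specified as primary. PP membership is decided after randomisation. The trial is open-label, only the Medtrum arm switches to a new device (Protocol 3.1.8), and the reasons for withdrawal include device malfunction, patient decision and the investigator's clinical judgement (Protocol 6.4). Exclusions can therefore differ between arms. If patients who do badly after the switch leave the PP set, the Medtrum mean falls and the comparison moves towards superiority.

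At stake is the strongest claim the trial can make. As the SAP stands, that claim could be made without support from any analysis of patients as randomised.

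**Working it through.** **1. The plan's own figures.** Inputs from SAP 5.1: "Risk of first kind: 2.5"%, "Statistical power: 80"%, margin 0.4, and "Assumed value of the difference between the two pumps: 0". The planning SD is 0.55 and the blinded-review SD is 0.8.

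n per arm = 2 × (1.960 + 0.842)² × SD² / 0.4²

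- SD 0.55: 29.7, so 30 per arm (60 in total); 60 / 0.8 = 75 randomised.
- SD 0.8: 62.8, so 63 per arm (126 in total).

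All match. These figures size non-inferiority. The documents give none for superiority.

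**2. Superiority rule without selective exclusion.** Assume the 100 included patients split 50:50, SD 0.8 and no baseline adjustment. SE = 0.8 × √(2/50) = 0.16. The observed Medtrum minus Omnipod difference must be below -0.3 - 1.96 × 0.16 = -0.61. If the true difference is 0, the chance of this is Φ(-0.614/0.16), about 0.006%.

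**3. Moderate selective exclusion.** Assume 5 of 50 Medtrum patients leave PP, their eHbA1c is 0.5 to 1.0 above that of the rest of their arm, and Omnipod loses none.

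- Shift in the PP difference: 5 × 0.5 / 50 = 0.05 to 5 × 1.0 / 50 = 0.10, in Medtrum's favour.
- SE = 0.8 × √(1 - r²) × √(1/45 + 1/50). This is 0.164 with r = 0 and 0.117 with r = 0.7. The baseline correlation r is not in the documents, so a range is used.
- Error at a true difference of -0.3: Φ(-1.96 + shift/SE).
- Error at a true difference of 0: Φ(-1.96 - (0.3 - shift)/SE).

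| Shift | SE | True difference -0.3 | True difference 0 |
|---|---|---|---|
| 0.05 | 0.164 | 4.9% | 0.025% |
| 0.10 | 0.164 | 8.8% | 0.07% |
| 0.05 | 0.117 | 6.3% | 0.002% |
| 0.10 | 0.117 | 13.4% | 0.012% |

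The nominal one-sided rate at -0.3 is 2.5%.

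**4. Extreme selective exclusion.** This was simulated with 20,000 trials per case, 50 per arm, true difference 0, normal outcomes, SD 0.8 and an unadjusted 95% interval. The worst k Medtrum values were removed.

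| k of 50 removed | Bias | False superiority at -0.3 |
|---|---|---|
| 2 | -0.07 | 0.06% |
| 5 | -0.15 | 0.3% |
| 10 | -0.27 | 2.1% |
| 15 | -0.39 | 9% |
| 20 | -0.51 | 24% |

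Ten of 50 is the planned 20% non-analysable share, taken as entirely selective and in one arm only. With residual SD 0.55 it gives 0.3%, and with 0.4 about 0.03%. With a threshold of 0 instead of -0.3, removing 5 would give 17-18% and removing 10 about 43%. The -0.3 threshold therefore supplies most of the protection.

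**5. Sign of the contrast.** Steps 2 to 4 use Medtrum minus Omnipod, as in SAP 5.1. SAP 7.4.1 writes Omnipod-Medtrum. Read literally, an upper bound below -0.3 would then mean that Medtrum is worse, and removing poor Medtrum outcomes makes the rule harder to meet (no such result in the simulations with exclusions).

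**The case against.** **The protocol does not simply assign this endpoint to ITT.** A reader might infer that the SAP contradicts a plain ITT rule for efficacy. The documents do not support that. The protocol summary's next sentence makes the primary endpoint PP first, and the general efficacy wording is absent from section 11.2.1. What stands is narrower: no protocol text gives superiority to PP alone, and the ITT validation it does require is missing from the SAP.

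**PP-only superiority is an inference.** The SAP names no population, and the ITTm run would show readers whether the result holds outside PP. That is correct. But ITTm is labelled sensitivity, omits four patients, fills gaps with a single mean or median, and cannot block a claim.

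**The threshold protects.** A reader might also infer that PP exclusions would probably produce a superiority claim for equal pumps. The calculations show otherwise: even losing the 10 worst of 50 Medtrum patients leaves the rate at about 2%, under the nominal level. The 5-13% range applies where Medtrum truly is better by 0.3, so the error there is overstating a real advantage.

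**The exclusion pattern is hypothetical.** The documents list no major deviations and give no evidence of imbalance between arms. This stands; the figures show sensitivity and do not predict anything.

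**Conclusion.** The point holds as a gap in specification with a modest, directional risk. The superiority population is unstated, the only model is PP, the confirmatory role that the protocol gives ITT has become a non-binding ITTm sensitivity run, and SAP section 6 does not record the change.

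The size depends on where the truth lies. With equal pumps, a false claim is rare: below 0.1% with five moderately worse Medtrum patients excluded, and about 0.3% with the five worst excluded. At a true difference of -0.3, the moderate exclusions raise the one-sided error from 2.5% to about 5-13%. These figures assume 50 per arm, SD 0.8, baseline correlation between 0 and 0.7 for the moderate case, one-sided selective exclusion, and the Medtrum minus Omnipod direction. The change is worth making because the claim should rest on the randomised comparison and the cost is small. The documents do not show that a false claim is likely.

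**What to change.** In SAP 7.4.1:

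- State that superiority is tested and claimed in the ITT population of section 7.1.3 (randomised patients who used the pump at least once, analysed as allocated), with the same baseline-adjusted ANCOVA. PP superiority is supportive only.
- Write the contrast as Medtrum minus Omnipod, consistent with section 5.1, and name Omnipod as the control level in the code.
- Keep the available eHbA1c data from patients with deviations or early pump discontinuation. Without this, the ITT model would lose many of the same patients. State how patients with no value are handled.

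Also align the two ITT definitions, since the derived-variable table in SAP 4.4.3 requires the eligibility criteria to be met and section 7.1.3 does not. Record the change in section 6.

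The cost is a few SAP sentences and one more model run, with no new patients or measurements. The downside is a possibly less favourable superiority result.
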